#### *5.8.1.4.2 Other cardiovascular stopping criteria*

- If participant presents with a QTcF of > 500 ms (females) or > 480 ms (males) at any time throughout the study, as measured and documented by 12-lead ECG, a re-test should be performed at the same visit. If at re-test, QTcF is confirmed > 500 ms (females) or > 480 ms (males), the participant must be permanently discontinued from study treatment. Participants with QTcF prolongation should be monitored until the absence of the persisting ECG abnormality can be confirmed.
- Symptomatic bradycardia or hypotension (e.g., syncope) at any time.

If any of those criteria are met, it will be recorded as an AE/SAE, and follow-up monitoring will have to be provided until the AE resolves and the participant's condition is stable.

### **5.8.1.5 *Infections***

In the event of a serious infection as per the investigator's opinion (e.g., opportunistic infection or serious infection requiring i.v. medication or hospitalization), the participant should be adequately treated and monitored until resolution of the infection. The investigator should consider permanent discontinuation of study treatment. The decision to

permanently discontinue study treatment should be made after evaluation of all available information concerning all potential causes of infection and based on the clinical status of the participant and response to the treatment of the infection. Further diagnostic work-up and consultation with an infectious disease specialist or other specialist should be considered according to local practice and the clinical situation.

These AEs must be reported in the eCRF [see Section 8.2]. Concomitant immunomodulatory medications may also be discontinued at the discretion of the investigator.

**Note:** Participants should not receive any of the per-protocol prohibited systemic treatments during 6 months after last study treatment intake, unless clinically indicated and justifiable in the opinion of the investigator.

#### **5.8.1.6 *Lymphocyte count monitoring***

Lymphocytes are assessed by the central laboratory at each scheduled visit.

##### **Alert for total lymphocyte $< 200$ cells/ $\mu$ L (i.e., $0.2 \times 10^9$ cells/L or $0.2 \times 10^3$ cells/ $\mu$ L)**

At any time throughout the study, when total lymphocyte count is  $< 200$  cells/ $\mu$ L, an alert including the lymphocyte count results will be generated by the central laboratory. This alert will be distributed to the investigator and to the sponsor. The sponsor will ensure that the investigator/delegate has received the alert. The investigator/delegate will take appropriate action to ensure the safety of the participant [see Figure 2]. The investigator must closely follow up with the participant, especially focusing on signs or symptoms of infection. The participant must be instructed to contact the study site if symptoms of infection occur [see Section 5.8.1.5].

Upon receipt of the first alert, the investigator/delegate will rapidly contact the participant to schedule a visit at study site as detailed below, while asking the participant to continue taking the study treatment.

At this visit, a lymphocyte count re-test and necessary clinical assessments will be performed. The central laboratory must be used for assessments of the re-test lymphocyte count.

##### **Re-test result is $\geq 200$ cells/ $\mu$ L (i.e., $0.2 \times 10^9$ cells/L or $0.2 \times 10^3$ cells/ $\mu$ L)**

The participant can continue taking study medication and can resume the regular schedule of visits as per protocol.

##### **Re-test result is 100 to $< 200$ cells/ $\mu$ L**

The participant must be retested within 2 weeks, while continuing to take study treatment.

[figure not shown]
### Re-test result is $< 100$ cells/ $\mu$ L (i.e., $0.1 \times 10^9$ cells/L or $0.1 \times 10^3$ cells/ $\mu$ L)

The participant must be permanently discontinued from study treatment, except at the first occurrence of a total lymphocyte count at re-test  $< 100$  cells/ $\mu$ L, in which case the participant must be re-tested within 1 week. Then, based on the results:

- If the lymphocyte count at 1-week re-test is confirmed  $< 100$  cells/ $\mu$ L, the participant must be permanently discontinued from study treatment. For results of 100 to  $< 200$  cells/ $\mu$ L or  $\geq 200$  cells/ $\mu$ L, see instructions above.

**Note:** If the lymphocyte count  $< 200$  cells/ $\mu$ L is accompanied by signs of opportunistic infection or severe infection (as per investigator's judgment), the study treatment will be permanently discontinued. The participant will be medically followed [see Section 5.8.1.5].

**Figure 2** Guidance for re-test results of lymphocytes  $< 200$  cells/ $\mu$ L

[figure not shown]
### Total lymphocyte count at final study visit

If the lymphocyte count is  $< 500$  cells/ $\mu$ L at FSV (i.e., after 6 months FU period or at the end of PTOP/FU period for participants who permanently discontinued study treatment), monitoring of clinical status and total lymphocyte count in local laboratory should be performed on a regular basis (e.g., every 2–4 weeks) until the lymphocyte count has returned to  $\geq 500$  cells/ $\mu$ L.

#### 5.8.1.7 Liver enzyme abnormalities

In the event of elevated transaminase  $> 3 \times$  ULN, the participant will be closely observed, liver tests will be repeated, and study treatment must be permanently discontinued, according to the guidance provided in Figure 3.

**Figure 3** Guidance for monitoring liver test abnormalities

\* Symptoms include unusual lethargy or fatigue, nausea, vomiting, right upper quadrant pain or tenderness, jaundice, anorexia, dark urine, fever, rash, itching and/or eosinophilia (> 5%).

\*\* See details below for participants receiving or not receiving anticoagulants.

ALT = alanine aminotransferase; AST = aspartate aminotransferase; INR = international normalized ratio; LT = liver test; TBIL = total bilirubin; ULN = upper limit of normal.

When marked abnormalities for AST, ALT, TBIL, or INR are reached as indicated in Figure 3, an alert will be sent by the central laboratory to the site/investigator and the sponsor. If a participant has ALT or AST  $\geq 3 \times$  ULN and is not receiving an anti-coagulant, then the threshold to permanently discontinue study treatment is  $1.5 \times$  ULN for INR. If a participant has ALT or AST  $\geq 3 \times$  ULN and is receiving an anti-coagulant (e.g., coumadin), then the threshold for INR is  $1.5 \times$  the upper INR target set for the participant (for example, if a participant is receiving coumadin with an INR target of 2 to 3, the marked abnormality for the INR would be 4.5 for this participant). The sponsor will contact the site/investigator to ensure that he/she will immediately contact the participant to enquire about symptoms and ask the participant to permanently discontinue study treatment or to return to the site within 72 h at the latest to repeat the test at the central laboratory (unless the clinical situation mandates immediate local testing) as applicable.

In the event of repeated abnormal liver tests within 72 h, the participant will be closely monitored, and liver enzyme and bilirubin tests will be repeated by the central laboratory

or locally according to the scheme illustrated in Figure 3. Further diagnostic work-up and consultation with a hepatologist or other specialist should be considered according to local practice. Preferably, the central laboratory should be used. If the local laboratory is used for testing in some situations (e.g., laboratory result needed immediately by treating physician), please ensure that an additional sample is sent to the central laboratory at the same time.

In all cases of permanent study treatment discontinuation, follow-up monitoring must be conducted until abnormalities in the liver assessments have resolved or are steadily improving.

#### **5.8.1.8 *Ocular abnormalities***

Suspected macular edema cases will be submitted to the IOSB [see Section 4.4].

The study treatment must be temporarily interrupted during the case assessment. If the IOSB confirms or suspects macular edema, study treatment must be permanently discontinued. If the IOSB assesses the case as not being a macular edema, the study treatment can be re-started. The participant must be followed up until resolution or until the condition is considered not clinically significant by the investigator.

#### **5.8.1.9 *Initiation of forbidden concomitant medication during the study***

At any time throughout the study, study treatment will be permanently discontinued if the participant starts taking a forbidden concomitant therapy [see Section 6.2.3].

#### **5.8.1.10 *Other potential permanent treatment discontinuation***

In the event of malignancy, study treatment will be permanently discontinued and the participant must be medically followed up as appropriate.

#### **5.8.1.11 *Other study-specific criteria for re-initiation after temporary treatment interruption***

The following guidance is provided for re-initiation of study treatment after study treatment interruptions.

A study visit to re-initiate treatment is only required after a study treatment interruption lasting more than 7 consecutive days and occurring between Day 1 and Day 14 of the study.

- During the period between Day 1 and Day 14, if the participant fails to take the dose for more than 7 consecutive days, the participant must inform the investigator and a re-initiation visit should take place no later than 7 days after the investigator is aware of the treatment interruption. Re-initiation of study treatment must be monitored on site following the cardiac assessment schedule and applying the discharge criteria as on Day 1 [see Appendix 5].

- If, at any visit (scheduled or unscheduled), the participant reports to the investigator that he/she missed taking the dose for one or more days during the initial 2 weeks of treatment (Day 1 to Day 14) but then resumed study treatment without reporting the interruption promptly, information on any event potentially related to the study treatment interruption should be collected. The participant should be counseled on the risks of non-compliance. Information on the treatment interruption must be recorded in the eCRF. No re-initiation visit needs to be performed in such a case.

If the participant misses doses after Day 14, a re-initiation visit is not required. Information on any event potentially related to the interruption should be collected and the participant should be counseled on the risks of non-compliance. Information on the treatment interruption must be recorded in the eCRF. Participants must be instructed to contact the investigator immediately if they experience any symptoms that may be related to bradycardia (e.g., dizziness, vertigo, syncope).

### **5.8.2 Measures for participant retention**

Participants withdrawn from study treatment are encouraged to remain in the study until its completion.

In order to ensure study data integrity and completeness, participants that are prematurely discontinued from study treatment should perform the subsequent visits as per PTOP schedule [see Table 3].

The investigator is encouraged to explain to the participants the importance of remaining in the study for data accuracy purposes and scientific relevance of the study results. The ICF will also highlight the scientific importance of the participant's data.

### **5.8.3 Withdrawal from the study**

Participants may voluntarily withdraw from the study without justification for any reason at any time. Participants are considered withdrawn if they state an intention to withdraw further participation in all components of the study (i.e., withdrawal of consent), die, or are lost to follow-up [see Section 5.8.4]. If a participant withdraws consent for further study participation, no further data will be collected in the eCRF from the date of withdrawal onward.

If, for whatever reason (except death or lost to follow-up), a participant withdraws from the study, the investigator/delegate should make their best effort to schedule a last appointment / telephone call to assess the safety and wellbeing of the participant, collect unused study treatment, and discuss follow-up medical care. Data obtained during this last appointment / telephone call will be recorded in the participant's medical records but will not be collected in the eCRF.

The main reason for premature withdrawal from the study must be documented in the eCRF.

The investigator must provide follow-up medical care for all participants who withdraw from the study, or must refer them for appropriate ongoing care, as described in Section 6.3.

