#### ***6.1.5.4 Study treatment accountability***

The inventory of study treatment dispensed to and returned by the participant (i.e., study treatment accountability) must be performed by site personnel on the day of the visit and before dispensing further study treatment. The inventory is to be recorded by site personnel in the site documentation and in the eCRF. The study treatment accountability log in the eCRF will include the following information for each study treatment bottle dispensed to the participant:

- Dispensed bottles number.
- Date dispensed / number of tablets dispensed.
- Date returned / number of tablets returned.

All study treatment supplies, including partially used or empty bottles must be retained at the site.

If the participant forgets to bring the remaining study treatment to a study visit, he/she must be instructed to not take any tablets from the remaining study treatment bottle and to return it at the next visit.

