## **8.2 Reporting procedures**

### **8.2.1 Reporting adverse events**

The occurrence of an AE may come to the attention of study personnel during study visits, telephone calls, or interviews with participants presenting for medical care.

At each study visit (scheduled or unscheduled), the investigator/delegate will inquire about the occurrence of AEs since the last visit.

All AEs with an onset date after signing the ICF and up to 6 months after study treatment discontinuation must be recorded in the eCRF.

The AE should be reported as a final diagnosis (if possible) rather than a list of symptoms.

Information to be collected on an AE form in the eCRF includes date of onset, action taken with the study treatment (e.g. dose reduction or suspension), outcome of AE, date of resolution (if applicable), and investigator/delegate's assessment of intensity as well as relationship to study treatment, study design or protocol-mandated procedures.

Information on worsening of intensity will be collected on a new AE form. If the AE lessens in intensity, no change in the severity is required to be reported.

AEs still ongoing after study treatment discontinuation must be followed up until resolution, until they are no longer considered clinically relevant, or until stabilization.

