### **9.2.1 Analysis of safety endpoints**

Descriptive analysis of safety endpoints will be performed using the SS (see definition in Section 9.1.2).

If not otherwise stated, only treatment-emergent safety data will be considered in tables and figures. Treatment-emergent safety data will be defined as assessments (or events) that were performed (or started) on or after the first study treatment intake (inclusive) up to the last study treatment intake + 180 days (inclusive).

Analyses on marked abnormalities for ECG and laboratory variables and Notable BP abnormalities will be specified in the SAP.

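### Section 5.8.3 keeps AEs and tablet counts learned at the last contact after consent withdrawal out of the eCRF, although Sections 8.2.1 and 6.1.5.4 require them there

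*Combined protocol and SAP*

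**What the plan says.** Section 5.8.3 counts a participant as withdrawn after withdrawal of consent, death or loss to follow-up. After withdrawal of consent, "no further data will be collected in the eCRF from the date of withdrawal onward". The next paragraph applies where, "for whatever reason (except death or lost to follow-up), a participant withdraws from the study". Once death and loss to follow-up are set aside, that leaves withdrawal of consent. The investigator is to try to arrange a last appointment or "telephone call to assess the safety and wellbeing of the participant", and to collect unused study treatment. Data from this contact go to the participant's "medical records but will not be collected in the eCRF". One item is still captured: "The main reason for premature withdrawal from the study must be documented in the eCRF".

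Two other sections set general rules without an exception for withdrawal:

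- Section 8.2.1: "All AEs with an onset date after signing the ICF and up to 6 months after study treatment discontinuation must be recorded in the eCRF".
- Section 6.1.5.4, on tablets dispensed and returned: "The inventory is to be recorded by site personnel in the site documentation and in the eCRF".

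Safety and tolerability is a primary objective (Section 3.1). Section 9.2.1 summarises TEAEs as the number and percentage of participants in the Safety Analysis Set (SS), which Section 9.1.2 defines as everyone who took at least one dose.

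**The concern.** The bar in Section 5.8.3 depends on when information is obtained, not on when the event happened. An AE that began while the participant was on treatment and under consent, but is first mentioned at the last contact, is inside the scope of Section 8.2.1 and outside the eCRF under Section 5.8.3. The same holds for the tablets handed back at that contact.

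The resulting error can go only one way. The participant has been dosed and so stays in the SS denominator, while the event drops out of the numerator. In a first evaluation of this drug in Chinese patients, with about 15 participants and descriptive percentages as the main safety output, one missing case can decide whether an event type appears in the summary at all. Sites may also resolve the conflict differently, which would make AE capture depend on the site.

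**Working it through.** **The rules side by side**

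| Item first learned at the last contact | Section 5.8.3 | Other section |
|---|---|---|
| Non-serious AE, onset on or before withdrawal | Medical records only | 8.2.1: eCRF |
| SAE, onset on or before withdrawal | Medical records only | 8.2.1: eCRF; 8.2.2: also an SAE form to Drug Safety within 24 h |
| Returned tablets | Medical records only | 6.1.5.4: eCRF |
| Event with onset after withdrawal | Not in eCRF | 8.2.1 as worded: eCRF; the consent position supports leaving it out |
| Main reason for withdrawal | eCRF | No conflict |

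The first three rows are direct conflicts. The fourth is a conflict of wording only, because Section 8.2.1 does not state the limit that withdrawal of consent imposes.

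**Length of the exposed interval.** Section 8.2.1 has AEs asked about at each visit, covering the time since the last one. Table 2 schedules treatment visits 30 days apart by nominal day. What is at risk is therefore what arose since the last visit, usually about one month, plus anything not mentioned earlier. AEs recorded at earlier visits stay in the eCRF.

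**Size.** The plan states no figure to reproduce: Section 9.4 gives about 15 participants without a derivation, and no withdrawal rate is given. The following is for scale.

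- One participant: 1/15 = 6.7 percentage points. Two: 2/15 = 13.3. Three: 3/15 = 20.0.
- Section 9.2.1 counts a participant once per AE category, so the full 6.7 points is lost only where that participant has no other record in the same category.
- Exact (Clopper-Pearson) 95% intervals for x of n = 15, with lower limit the 0.025 quantile of Beta(x, n − x + 1) and upper limit the 0.975 quantile of Beta(x + 1, n − x): 0/15 gives 0 to 21.8%; 1/15 gives 0.2 to 31.9%; 2/15 gives 1.7 to 40.5%. One unrecorded case moves a result by one step along this list.

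The chance that at least one AE is lost is 1 − (1 − q)^w. Here w is the number of consent withdrawals and q the chance that a withdrawing participant first discloses an AE at the last contact. Both are assumptions:

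| w | q = 0.10 | q = 0.25 | q = 0.50 |
|---|---|---|---|
| 1 | 10% | 25% | 50% |
| 2 | 19% | 43.8% | 75% |
| 3 | 27.1% | 57.8% | 87.5% |

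**The case against.** The strongest defence is that Section 5.8.3 is a deliberate consequence of consent. The last contact takes place after consent has been withdrawn, and a specific rule for such participants can be read as qualifying the general rule in 8.2.1. This stands for events that begin after withdrawal. It does not settle events that began earlier, because neither section says which one prevails. What the consent form permits cannot be checked, since consent pages are not in the public copy.

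A second defence is that other routes limit the loss. SAEs have their own form (8.2.2). Central laboratory and ECG results reach the sponsor from the vendors (10.6.2), so abnormalities already measured are kept. The main withdrawal reason is in the eCRF. All of this stands, and it is why the gap is mainly one of non-serious AEs. A withdrawal reason is still not an AE record with onset, intensity and causality, and an SAE on a form but barred from the eCRF would leave the two databases in disagreement.

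Three stronger readings are tempting, and the documents do not support them:

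- *That the lost events come from the participants most likely to leave because of them.* Under Section 5.8.1.1, someone who stops treatment, including for an AE, is not withdrawn from the study. That participant has a premature end-of-treatment visit within 7 days and then observation visits, each with AE collection (Table 3). Some people may stop treatment and leave the study together, but nothing shows that AEs drive this.
- *That the treatment-emergent window is distorted if the last-intake date is first learned at this contact.* The window closes 180 days after last intake. A participant who withdraws while on treatment has no later eCRF data, so every recorded post-dose event is inside it already. The date matters for describing exposure.
- *That rates of AEs leading to discontinuation are biased downward.* The main reason for permanent discontinuation must be in the eCRF (5.8.1.1), so this bias is possible but not shown.

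Finally, the analysis is descriptive with no decision threshold, and the intervals for neighbouring counts overlap almost entirely. That limits the consequence of one lost case but does not remove the contradiction.

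**Conclusion.** The contradiction is real and narrow. Section 5.8.3 as written excludes from the eCRF AEs with onset on or before withdrawal, and returned tablet counts, that Sections 8.2.1 and 6.1.5.4 require there. Only withdrawal of consent from the whole study is affected, and only information first obtained at the last contact. The consequence for the primary safety summary is a possible undercount of up to 6.7 percentage points per affected participant and AE category, with the denominator unchanged. How many participants would be affected cannot be estimated from the documents, so the larger figures above rest on assumed numbers of withdrawals and disclosures. The tablet count bears on compliance (6.1.6), not on an endpoint in Section 9. This is a gap in data collection that merits a short correction; it is not evidence that the planned safety results will be materially biased.

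**What to change.** Change two places in Section 5.8.3 together, since changing only one would leave the section contradicting itself:

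1. Qualify the sentence that stops eCRF collection from the withdrawal date by adding: *except for information on the period up to and including that date, as set out in the next paragraph.*
2. Replace the last-contact sentence with: *Provided the participant agrees and local law permits, the following information from this contact is entered in the eCRF: AEs and SAEs that began on or before the withdrawal date, the date of the last dose taken, and the number of tablets handed back. Events that began after the withdrawal date are not entered.*

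Then state the remaining exception in Section 8.2.1, cross-refer to Sections 6.1.5.4 and 8.2.2, and align the consent form. It would also help if the SAP reported the number of consent withdrawals, their recorded reasons, and follow-up time after the last dose, so that readers can judge how much could be missing.

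The cost is a few lines of protocol and consent text, with no new visit or procedure. The amendment page for V3.0 records no participants enrolled; if that is still so, nobody would need to re-consent. The downside is that a participant who is leaving must be asked for agreement, and data from those who refuse remain uncollected.
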